**3 Study sponsor**

Merck, S.A.

PPD

**4 Study objective**

*The study objective is to verify through a single dose study, if the test formulation of Levothyroxine sodium presents an equivalent rate and extension of absorption to the comparator formulation when administered with the same dosage and under fasting conditions and after baseline correction concentrations.*

PPD

**5 Study design**

*Every study is designed in order to allow that primary pharmacokinetic parameters estimations ( $C_{max, adj}$ ,  $AUC_{0-72, adj}$ ) are obtained free from the interference of any foreign factor that might negatively influence the comparison between the formulations. This way, the search for the*

standardization of the research subjects conditions will be attempted once only through this standardization there will be confidence enough to reach the final conclusion if both drugs are bioequivalent or not when given in the same conditions.

PPD

### 5.1 Type

Single center, open-label, cross, randomized, prospective, two treatments (A and B), two periods, 2 subgroups, two sequences (AB and BA), truncated, using 72 healthy research participants, with ages ranging between 18 and 50 years old. The participant will receive, at each period, the test formulation or the comparator formulation according to the randomization list (Annex 6) under fasting conditions. According to the resolution RE # 1170, dated April 19, 2006, the interval between periods (washout) must be of, at least, seven elimination half-lives of the drug and/or metabolite. The drug mentioned, Levothyroxine sodium, have a half-life of approximately 6 to 7 days, therefore, the washout period of the study should be at least 65 days to guarantee that the drug has been completely eliminated from the body, but according to PPD experience, the washout will be 65 because in a previous trials in the PPD showed a significant effect of levothyroxine (T4) in the 2 period independently of the randomization method (probably due to the TSH suppression and consequently decrease of endogenous levels of levothyroxine).

According to the resolution RE # 1170, dated April 19, 2006, letter "q", in the case of drugs that show half-life long (more than 24 hours) can be used an alternative collection chronogram, a minimum of 72 hours which allows the determination of the truncated area under the curve ( $AUC_{0-72, adj}$ ).

In this study, for the drug will be conducting Levothyroxine sodium truncation in 72 hours considering the value of the half-life of approximately 6 to 7 days.

## 6 PPD / Study population

PPD

PPD

**6.1 Detailed description**

*At least 72 research participants (36 male and 36 female) of ages between 18 and 50 years old. The BMI - Body Mass Index of the participants must be comprised within the range of 18,50 to 24,90, for this study will be accepted a range of 18,50 to 27,00. ). There are no restrictions regarding the ethnic group.*

PPD

**6.2 Research Participant screening**

*The research participants will be recruited among those who visit the PPD Clinical Site. Before being submitted to any evaluation, the participants will have all the questions answered, and if they agree, they will sign the recruitment and research participants screening form which was approved by the Ethics Committee in Research of the Institute of Pharmaceutical Sciences - PPD accredited by the National Commission for Ethics in Research (CONEP) CNS/MS.*

**6.3 Triagem**

PPD

PPD

### 6.3.1 Clinical evaluation

According to SOP CLIN 006 (Research Participant Recruitment and Selection) PPD clinical evaluation will be divided in phase 1 and phase 2. The physician and/or nurse should first realize phase 1 of the clinical evaluation and if the participant is considered apt will go through phase 2 of the clinical evaluation. If the participant is considered unapt in the phase 1 will not go to phase 2: it may be dismissed immediately by the physician and/or nurse or go through treatment.

When the Research Participant goes to treatment may be allocated for months and come back for accompanying many times. It will be realized phase 2 of the clinical evaluation only when the participant becomes apt.

After phase 2 of the clinical evaluation by a physician, the Research Participant will have 3 months to realize the first laboratorial exams. It is necessary to highlight, that in each time the participant visits PPD for accompanying of the treatment the clinical evaluation for phase 1 will be revised and actualized.

In the clinical evaluation, the candidates to Research Participant should not present signs or evident symptoms of any cardiac, hepatic, renal, pulmonary, neurological, gastrointestinal or hematological disease. To verify it will be realized an anamnesis, as well as the evaluation of the biochemical and hematological laboratorial exams as related in item 6.3.2.

During the clinical evaluation, the Research Participant will be classified according to the racial group they belong. To this race classification will be used the auto declaration method, in which the subject will auto declare as part of a racial group according to the following definitions: white, black, mulatto, yellow or Indian. The physician and/or nurse has to register the declared racial group in the clinical evaluation form.

The Research Participant will only be accepted in the study if they are considered healthy as determined by the clinical evaluation and in the laboratory exams done before the beginning of the study and if they satisfy the criteria established in items 6.4 and 6.5. The laboratorial exams done in the pre study period will be valid for 3 months and the electrocardiogram will be performed 7 days prior to period 1 of confinement.

After proved the state of health, they will be submitted to an interview with the doctor to evaluate their mental health, as well as the emotional state to participate in the investigation.

PPD

PPD

### 6.3.2 Clinical and lab tests

The Research Participants will be submitted to the following clinical and lab tests:

- Electrocardiogram (12-leads);
- Testing for alcohol at the time the Research Participant arrives to the hospital during periods 1 and 2;
- Testing for drugs of abuse at the arrival of the Research Participant to the hospital in periods 1 and 2;
- Pregnancy test on arrival for Research Participant hospitalization during periods 1 and 2;
- Blood tests: complete blood count (erythrogram and leukogram);
- Chemical tests: urea, creatinine, bilirubin (total and fractions), total proteins, albumin, blood glucose, alkaline phosphatase, SGOT, SGPT, total cholesterol, triglycerides and uric acid;
- Tests: free and total T3 and T4, TSH;
- Serological tests: hepatitis B (HBsAg and IgM Anti HBc), hepatitis C, HIV 1 and 2;
- Urinalysis;
- Serum  $\beta$ HCG test for women.

Obs: Hepatitis B, hepatitis C, and HIV 1 and 2 tests will be performed only during the pre-study period. Test Pregnancy for women will be repeated at the moment of hospitalization (Period 1 and 2) by urine dipstick.

[figure not shown]
Drugs likely to be detected in drug testing are: Methamphetamine, Opiate, Morphine, Tetrahydrocannabinol – THC (Marijuana), Amphetamine, Benzoyllecgonine (Cocaine) and Benzodiazepine.

PPD will provide a copy of the pre-study and post-study lab tests to the research participant.

The clinical and lab tests files, the CRFs, dossiers, and charts will be stored by the PPD for at least 10 years, according to Resolution – RDC # 56 dated 8/oct/2014. Whenever needed, due to some complication, PPD will provide a copy of the papers to the research participant.

PPD

PPD

#### **6.4 Inclusion criteria**

*The following criteria must be satisfactory to the research participants can be included in the study:*

- 1 To have freely agreed and signed the consent form, after all essential elements of the protocol have been clarified, before any procedure.*
- 2 Healthy males and non-pregnant females volunteers.*
- 3 Between 18 and 50 years old.*
- 4 BMI - Body Mass Index of the research participants must be comprised within the range of 18.50 to 27.00.*

- 5 *No abnormal findings on medical history that, in the opinion of the investigator, constitutes a risk or a contraindication for the participation of the subject in the study or that could interfere with the study objectives, conduct or evaluation.*
- 6 *Normal vital signs: heart rate between 50 and 100 beats per minute; Systolic pressure between 80 and 129 mmHg; diastolic pressure between 50 and 89 mmHg; temperature between 36.0 and 37.0 ° C.*
- 7 *Electrocardiogram [ECG] normal (Abnormalities, even if clinically not relevant, are not permitted (e.g. PR, QRS, QT, QTcF should be within normal range, no conduction abnormalities etc).*
- 8 *All values for biochemistry and hematology tests of blood and urine within the normal range or showing no clinically relevant deviation as judged by the Investigator.*
- 9 *Subjects with thyroid profile results within normal ranges (total and free T3 and T4, and TSH must be within normal ranges).*
- 10 *Biosafety tests negative for the presence of human immunodeficiency virus [HIV], hepatitis B [HBV] and Hepatitis C [HCV].*
- 11 *Subjects with negative results in screening tests for drugs of abuse such as amphetamines, benzodiazepines, cocaine, methamphetamines, morphine and tetrahydrocannabinoids.*
- 12 *Subjects with negative alcohol test.*
- 13 *Women with negative (qualitative and quantitative) pregnancy tests at screening and at admission in each period.*
- 14 *Subjects must not have a history of alcohol abuse (an average daily intake of more than 3 units or a weekly intake of more than 21 units where 1 unit equals 340 mL of beer, 115 mL of wine or 43 mL of spirits), psychoactive substances or chronic use of drugs.*
- 15 *Nonsmoker for at least 3 months.*
- 16 *All women of childbearing potential who are not pregnant or breastfeeding and who are using a highly effective contraceptive method (defined as those, alone or combined, which failure rate is low; i.e., less than 1 % a year, when used continuously and correctly) for at least one month before first and following last dosing. Barrier methods and intrauterine device are considered standard contraceptive methods. Hormonal methods will not be included. Post-menopausal women can be included (i.e., those with at least 12 consecutive months of amenorrhea following their last menstruation period) or surgically sterile/hysterectomy for at least 6 months before their participation in the study.*

PPD [redacted]

PPD

## 6.5 Exclusion criteria

Any of the following criteria below will exclude the study research participant:

- 1- Supplementary tests results out of the values considered as normal, unless considered clinically irrelevant;
- 2- Research participants who are submitted to surgery before the beginning of the study will be carefully evaluated by the doctor regarding the enrollment in the study complying to an exclusion period ranging from 4 to 8 weeks;
- 3- Positive test for hepatitis B, hepatitis C, or HIV in pre-study tests;
- 4- Subjects with a history of hypersensitivity/allergy to study drug or excipients, history or presence of asthma or any serious allergy (requiring hospitalization or prolonged systemic treatment), any food allergy or intolerance which in the opinion of the Investigator represents a safety risk (e.g. iodine allergy, etc.)
- 5- Has participated in any experimental trial or has taken any experimental drug within 6 months previous to this study (RDC Resolution # 34, dated June 3, 2008);
- 6- Subjects that prior to the dosing takes any other medication and had not passed at least seven half-lives of elimination of the drug, in this case, be considered by the Principal Investigator the non-inclusion of the subject in the study. Subjects taking medications known to affect thyroid hormone metabolism, e.g., oral contraceptives, hormonal implants, parenteral hormones, anabolic steroids, androgens, etc., or the bioavailability of levothyroxine like proton pump Inhibitors.
- 7- Has a history of alcohol abuse or has ingested alcohol 24 hours previous to the hospitalization period;
- 8- Has a history of drug abuse [patients using marijuana and hashish less than 3 months before the visit will be excluded. For drugs such as cocaine, phencyclidine (PCP), crack, heroin less than 1 year before the visit are excluded];
- 9- Subjects who have been exposed to agents known as inducers or inhibitors of hepatic enzyme systems or have potentially toxic medications taken within thirty days before the start of the study.
- 10- Use of monoamine oxidase (MAO) inhibitors (moclobemide, iproniazid, nialamide, phenelzine, tranylcypromine) two weeks before the beginning of treatment;
- 11- Use of serotonin reuptake inhibitors (duloxetine, milnacipran, nefazodone, venlafaxin, citalopram, escitalopram, fluoxetine, paroxetine, sertraline, fluvoxamine);
- 12- To present any psychiatric and/or psychological disease (including depression), unless considered clinically not significant by the clinical investigator;
- 13- Has a clinically significant history and/or presence of gastrointestinal disease (example: chronic diarrhea, intestinal inflammatory disease), present gastrointestinal symptoms (example: diarrhea, vomiting), liver or kidney disease, or other known condition that may interfere in the absorption, distribution, metabolism, or excretion of the drug. Research participants with episodes of

vomiting within 24 hours before the administration of the drug must be evaluated by the clinical investigator regarding the possibility of remaining in the study;

- 14- Subjects with a history of cardiovascular disease, kidney, liver, metabolic, gastrointestinal, neurological, endocrine, hematopoietic (any type of anemia), mental illness or other organic abnormalities that could affect the pharmacokinetics of the product under study.
- 15- Any surgical or medical condition, including findings in the medical history or in the pre-trial assessments, that in the opinion of the investigator, constitutes a risk or a contraindication for the participation of the subject in the trial or that could interfere with the trial objectives, conduct or evaluation;
- 16- Has donated or lost more than 450mL or more of blood within three months previous to the study;
- 17- Has any condition preventing her of participating in the study according to the investigator's judgment;
- 18- Being vegetarian or have dietary habits that preclude ingestion of diet offered in the study;
- 19- The participant is inability to remain seated (approximately 90 ° plan) for 1 hour after drug administration of the drug, or time required at the discretion of the clinical investigator;
- 20- Being heavy smoker less 3 months;
- 21- Thyroid function tests outside normal limits (TSH, free and total T4, free and total T3);
- 22- Positive  $\beta$ HCG test for women;
- 23- Breastfeeding women;
- 24- Women who are taking contraceptives, because they have interaction when administered concomitantly with the drug in question;
- 25- Subjects requiring any prescription or non-prescription medications during the course of the study, including multivitamins, nutritional supplements and herbal products that may affect the outcome of the study, with the exemption of occasional use of paracetamol not exceeding 1000mg/day for maximum of three consecutive days;
- 26- Subjects who have been hospitalized for any reason within sixty days before the start of the study or who have been seriously ill within thirty days before the start of the study;
- 27- Subjects that have smoked tobacco, cigarettes or consumed coffee, snuff or drinks containing xanthines (coffee, tea, cocoa, chocolate, matte, cola, etc.) such as caffeine, theobromine, theophylline, or charcoal-grilled foods among others, affecting the pharmacokinetics of the drug in assessment, at least within 24 h before the start of the study;
- 28- Subjects who have intaked of grapefruit, orange, cranberry or juices of these 3 fruits, from 7 days prior to drug administration until collection of last PK sample in each period;
- 29- All cases where the principal investigator considers failure to the protocol and can make questionable the result of the study (severe adverse reaction or serious event adverse, Indiscipline of the subject, failure diet, if emesis occurs within the time set by the  $t_{max}$ );
- 30- Unlikely to comply with the protocol requirements, instructions and trial-related restrictions; e.g., uncooperative attitude, inability to return for visits, and improbability of completing the trial;
- 31- Inability to communicate or cooperate with the investigator (e.g., language problem, illiterates, poor mental status) or to comply with the requirements of the entire trial, including dietary restrictions;
- 32- Subject is the principal investigator or any sub-investigator, research assistant, pharmacist, trial coordinator, other staff or relative thereof directly involved in the conduct of the trial.

PPD

#### **6.6 Restrictions and prohibitions: before, during and after the study**

1. *Always as possible, there should be avoided the use any kind of medication concomitantly with the study medication;*
- i. *Occasional use of paracetamol will be permitted within the screening period. The investigator may allow the subject to take paracetamol in case of pain during the trial, but the dose should not exceed 1000 mg/day for a maximum of three consecutive days. The amount of paracetamol administered must be recorded in the CRF. Any additional concomitant therapy that becomes necessary during the trial from the date of signature of informed consent and any change to concomitant drugs must be recorded in the corresponding section of CRF and in that case, the permanence of the subject in the study will be evaluated by the principal investigator.*
2. *Subjects should be non-smokers and will be instructed not to use any medication during the study and not to consume any alcohol, or xanthine-containing (coffee, tea, cocoa, chocolate, matte, cola, etc.) such as caffeine, theobromine, theophylline, or charcoal-grilled foods among others, affecting the pharmacokinetics of the drug in assessment within 24 hours before admission and through the study.*
3. *Chewing gum during confinement period;*
4. *The consumption of alcohol and energetic drinks will be prohibited in the 24 hours before the admission and through the study; Water will be permitted free except in the seven hours before and in the two hours after the administration of the medicine;*
5. *Ingestion of fried and fatty food during the confinement period;*
6. *To use food or drink that contains grapefruit (also known as toranja, pomelo, jamboa, laranja-melancia, pamplemusa, laranja-vermelha, laranja-romã) in the seven days before the beginning of each period up to the last collection of each period;*
7. *Soya and its derived can reduce the intestinal absorption of levothyroxine, so they are prohibited in the seven days before the beginning of each period up to the last collection of each period;*
8. *Procedures requiring use of iodinated contrast are prohibited in the 30 days before the beginning of the study;*
9. *To use vitamins or natural products (including garlic supplements) in the seven days before the administration of the medication until the last blood collection in each period of the study up to the last collection of each period.*

PPD

PPD

### **6.7 Criteria for the discontinuation or withdrawal of participants from the study**

The following criteria will be considered for the discontinuation of withdrawal of research participant from the study:

1. *Withdrawal of the subject's consent;*
2. *Occurrence of pregnancy;*
3. *Occurrence of adverse events leading the research participant to drop out of the study, such as unavailability or intolerance to the study procedures;*
4. *Adverse effects of the drug mentioned that are considered clinically significant by the physician in charge and/or harmful to the research participant's health;*
5. *Abnormal lab tests considered as clinical relevant;*
6. *Intercurrent diseases requiring medication;*
7. *Unfulfillment of the established rules;*
8. *Research participant present during the pre-admission (Period 1 or 2) tested positive for alcohol and/or drug test;*
9. *Research participant (for the women) present during the pre-admission tested positive for pregnancy test;*
10. *Chew the tablet during drug administration;*
11. *Study interruption;*
12. *Need to use some prohibited medication during the participation in the study;*
13. *To find out that the research participant does not meet the study requirements;*
14. *If the research participant take during the study any medication which contains the same substance which will be used as internal standard during the analysis of the plasma samples;*
15. *Research participant did not ingest the entire dose of the study drugs provided;*
16. *Research participant losing the last point of collection of the periods (period 1 or 2);*

17. All cases where the principal investigator considers failure to the protocol and can make questionable the result of the study (severe adverse reaction or serious event adverse, Indiscipline of the subject, failure diet);
18. Unlikely to comply with the protocol requirements, instructions and trial-related restrictions; e.g., uncooperative attitude, inability to return for visits, and improbability of completing the trial;
19. In case of vomiting or diarrhea episodes after the administration of the drug until two times the Tmax of the active ingredient and/or metabolite, regarding the pharmaco mentioned, Levothyroxine, research participants having episode of vomiting or diarrhea within 08 hours after the administration must be excluded.

PPD

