1.3.1 PPD / *Pharmacokinetic*

PPD

PPD

*Absorption: administered orally, levothyroxine absorption is incomplete and variable, around 50% to 80%, especially when administered with food. The ileum and colon are the sites where most of absorption takes place (MARTINDALE, 2002; KOYTCHEV, 2004; KOROKOLVAS, 2006; SILVA, 2006). This variation in absorption is dependent on several factors, such as: vehicles, intestinal flora, dietary, foods, concomitant medications (SILVA, 2006).*

*Following oral administration, the maximum plasma level of levothyroxine is reached from 2 to 4 hours. The ingestion of levothyroxine in fasting conditions increases its absorption (MARTINDALE, 2002).*

*Distribution: linked to plasma proteins (TGB, albumin and transthyretin) thyroxine is distributed in a volume of 10L (MARTINDALE, 2002; SILVA, 2006). Thyroid hormones cross the placenta and can be found in breast milk (MARTINDALE, 2002).*

*Metabolism: the metabolism of thyroxine occurs by deiodination and has as its product triiodothyronine (35%) (SILVA, 2006). Levothyroxine has a plasma half-life of 6 to 7 days (KOYTCHEV, 2004). According to Martindale (2002) levothyroxine is primarily*

metabolized in the liver and kidneys in T3 and about 40% is biotransformed in reverse (inactive) T3 and both undergo deiodination to form inactive metabolites.

Excretion: the untransformed T4 portion of T3 is eliminated by feces after conjugation with glucuronides and sulfate (SILVA, 2006). According to Martindale (2002) levothyroxine undergoes recirculation.

According to the Summary of Products Characteristics (2015, orally given levothyroxine is absorbed almost exclusively in the upper small intestine. Depending on the galenical formulation absorption amounts up to 80% and Ttmax is approximately 5 to 6 hours.

Following oral administration the onset of action is seen after 3-5 days. Levothyroxine exhibits an extremely high binding to specific transport proteins of about 99.97 %. This protein hormone binding is not covalent and so the bound hormone in plasma is in continuous and very rapid exchange with the fraction of the free hormone.

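### Do the differing vomiting windows in sections 6.5 and 6.7, and the two Tmax figures in section 1.3.1, leave the primary analysis set undefined?

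*Combined protocol and SAP*

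**What the plan says.** Four places in the combined protocol and SAP bear on this.

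- **Section 6.7, item 19** (discontinuation or withdrawal) opens with the general principle: "In case of vomiting or diarrhea episodes after the administration of the drug until two times the Tmax of the active ingredient and/or metabolite". The same sentence then turns to levothyroxine and gives the consequence: "research participants having episode of vomiting or diarrhea within 08 hours after the administration must be excluded".
- **Section 6.5, item 29** (exclusion criteria) is a catch-all: "All cases where the principal investigator considers failure to the protocol and can make questionable the result of the study". Its examples, in parentheses, include a case "if emesis occurs within the time set by the" Tmax. It gives no hours and does not mention diarrhea.
- **Section 6.7, item 17** repeats that catch-all with the examples "severe adverse reaction or serious event adverse, Indiscipline of the subject, failure diet" and leaves vomiting out.
- **Section 1.3.1** reports from one source that "the maximum plasma level of levothyroxine is reached from 2 to 4 hours" and from another that "Ttmax is approximately 5 to 6 hours".

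Section 13 analyses participants who finished all periods and refers to neither vomiting rule.

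**The concern.** Read side by side, the two items differ in three ways: the multiple of Tmax (one or two), the events covered (vomiting only, or vomiting and diarrhea) and the force of the rule (the investigator's judgement, or mandatory). The Tmax that the windows rest on also has two values. If each combination is treated as a live option, the window could be read as anything from 2 to 12 hours.

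That would matter because exclusion decides who enters the bioequivalence comparison. The study is open-label, and section 1.3.5 lists vomiting and diarrhea among the drug's reactions. A loose rule would let a site keep or drop a participant knowing which product had been given. The risk would be selective inclusion more than lost precision.

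**Working it through.** **1. The windows implied by the documents.**

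- Item 29, one times Tmax: 2 to 4 h, or 5 to 6 h.
- Item 19, two times Tmax: 2 × (2 to 4) = 4 to 8 h, or 2 × (5 to 6) = 10 to 12 h.
- Item 19 as stated for levothyroxine: 8 h.

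The stated 8 h equals 2 × 4 h, the top of the first range. It is 2 to 4 h shorter than twice the second range.

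**2. Whether the items conflict.** Within item 19, the two-times-Tmax clause carries no consequence of its own; the instruction to exclude attaches only to the 8 hours. It is therefore a single rule with a rationale. Item 29 reaches at most 4 h or 6 h, both below 8 h, and does not say that someone who vomits later stays in.

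| Event | Item 29 | Item 19 as stated | Can both be obeyed? |
|---|---|---|---|
| Vomiting within Tmax (up to 4 or 6 h) | investigator may judge a failure | exclude | yes |
| Vomiting at 7 h | silent | exclude | yes |
| Diarrhea at 3 h | silent | exclude | yes |
| Vomiting at 9 h | silent | outside the 8 h | yes |

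The 9 h case is disputed only if a reader sets the printed hours aside and recalculates them from the longer literature Tmax.

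**3. Whether section 13 reopens the question.** Take a participant who vomits at 7 h in period 2 and still gives the 72 h sample. Section 13 alone might seem to include this person. But item 19 is a withdrawal criterion, and a participant excluded under it is reasonably read as not having finished the study's periods.

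**4. Size.** The inputs from section 13.1 are CV 32%, true ratio 0.95, limits 80 to 125%, 5% significance level and a 2x2 crossover.

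- Within-subject SD on the log scale: √ln(1 + 0.32²) = √ln(1.1024) = 0.312.
- Standard error of the log ratio at n = 60: 0.312 × √(2/60) = 0.057, with 58 degrees of freedom.
- Exact power of the two one-sided tests, for one parameter:

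| Evaluable | 72 | 70 | 68 | 64 | 60 | 58 | 57 |
|---|---|---|---|---|---|---|---|
| Power | 0.948 | 0.943 | 0.937 | 0.924 | 0.908 | 0.899 | 0.894 |

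The plan's 60 is reproduced as the smallest balanced number reaching 90%, since 58 gives 0.899. The allowance is 60 × 0.20 = 12, so 60 + 12 = 72 are randomized. Exclusions under item 19 draw on those 12 places, along with every other cause of loss. Three further losses after all 12 were used would move power from 0.908 to 0.894, or 1.4 points.

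**The case for a change.** The best case for a change is that the protocol never says which Tmax the study uses. The sampling schedule is densest, every 15 minutes, from 3:00 to 5:00, which centres on 4 h and fits the printed 8. Half-hourly sampling continues to 6:30, however, so later peaks are also provided for. Participants stay in the unit until 12 h after dosing, so an event between 8 and 12 h would be seen and would need a decision. Section 14 leaves the handling of deviations to discussion and gives no criterion in advance. Section 13 does not point to item 19.

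Much of this stands as description. Items 29 and 19 were not kept aligned, item 19's basis fits only one of the two Tmax figures, and a cross-reference in section 13 would help.

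It does not show that the result depends on which passage is followed. Up to 8 h, item 19 leaves no discretion and makes no distinction by product or period. Item 29 sits among the entry criteria, and where its catch-all recurs in the withdrawal section, as item 17, the vomiting example is absent because item 19 deals with it. Section 13.3.3 also bars exclusion for purely mathematical or statistical reasons. The room for selective inclusion is therefore confined to events after 8 h that someone chooses to argue from a background Tmax figure, and the documents give no rate for such events.

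**Conclusion.** The concern does not call for a change to the plan. Followed as written, the protocol supplies one exclusion rule in hours, specific to this drug, mandatory, covering diarrhea and the same for both products. The passages around it are untidy but do not override it. The mismatch between the 8 hours and the 5 to 6 h Tmax, and between items 29 and 19, is an editorial inconsistency that the protocol's authors should reconcile. Nothing here says which window or Tmax is right.

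No effect on the bioequivalence conclusion is shown. On precision, power for one parameter runs from 0.948 with all 72 evaluable to 0.908 with 60.

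This rests on three assumptions: that item 19 is applied by its printed hours, that a participant excluded under it does not count as having finished all periods under section 13, and that the planning values of CV 32% and ratio 0.95 hold.
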